8 CHIVITT STUDY PROCEDURES/EVALUATIONS

8.1 Study Procedures

8.1.1 Admission/entry to a CHIVITT cohort

- Obtaining of informed consent or confirmation of signed informed consent
- Vital signs (including SpO₂, HR, RR, BP, and oral temperature) and height and weight will be obtained
- A targeted physical examination may be performed, as directed by the medical history, medications, and vital signs assessment. An absence of significant past medical history, concomitant prescription medications, and abnormalities in vital signs will not require a physical examination.
- Review and record medical history* and concomitant medications†.
 - *All significant past and current diagnoses will be documented. All signs and symptoms (regardless of severity) that the subject has experienced within 30 days prior to screening will be documented. Medication allergies will also be documented on this form.
 - †All prescription and non-prescription medications, alternative therapies, and vaccines taken within 90 days prior to screening or since the last study visit should be documented.
- For Donors and Recipients, performance of a multiplex influenza, SARS-CoV-2, respiratory virus panel test (e.g., BioFire Respiratory Virus panel)
- For Donors, collection of a respiratory sample for viral quantitation
- Venous whole blood (~10 mL) collection for HAI and FRNT assays and the storage of remaining volumes for secondary research
- For Recipients only, Nasal wash specimen (~5-10 mL) will be collected.
- Additional nasal swab and a saliva sample for research tests (Participants will be asked to collect a saliva sample using a standard protocol and by spitting into a screw cap specimen cup or 50 mL polypropylene screw cap tube).
- For Donors, Exhaled breath sampling within 24 hours of entry.
- Point of care urine pregnancy test for donor and recipient females of childbearing potential within 24 hours of admission to the hotel quarantine unit (to be completed prior to any exposure events)

8.1.2 Exposure Events

- Exposure events will be held in a large hotel room each lasting up to several hours. Each cohort will experience multiple exposure events over the course of their stay. Each exposure event will be either a high or low air hygiene exposure.
- Low air hygiene conditions will be limited by the quarantine hotel's standard mechanical ventilation (~0.7 air changes per hour) and may be further limited by sealing windows and or blocking bathroom exhaust fans and hallway supply as necessary to control carbon dioxide levels to simulate a poorly ventilated public space while remaining within the OSHA permissible exposure limit.
- High air hygiene conditions will supplement the building's mechanical ventilation with portable HEPA filter units and / or germicidal ultraviolet air disinfection (either upper-room 254 nm or direct 222 nm UV-C or similar technologies and wavelengths with monitoring to confirm compliance with current ACGIH Threshold Limit Values).
- The room in which the exposure events occur will have the ventilation rate, CO₂ concentration, temperature, and relative humidity continuously monitored and supplemental heating, cooling, and dehumidification will be supplied to maintain comfort (~20°C ± 3) and relative humidity <40%.
- Recipients will be randomized to spray-borne and touch transmission intervention (Intervention Recipients, IR) and control (Control Recipients, CR) within each exposure event, except that the initial exposure event may include only CR to assess the SAR and power of the study design for the remaining events.
- Prescribed group activities will be planned by the study team to involve close-distance interactions between study participants (donors and recipients). Due to the unpredictability of when donors may become available, it is intended to be flexible for the scheduling of these events for the time of day, duration, and frequency of number of days. For example, donors and recipients will engage in supervised playing of board games, watching films, eating meals together while ensuring that randomized designated IR individuals comply with spray-borne and touch transmission prevention interventions (face shield use, hand sanitization, and no-touch-face rules). Outside of the exposure events, donors and recipients are to be housed in separate rooms to prevent inadvertent "contamination" or transmissions outside of the prescribed group activities.
- The conditions of each exposure event, time, duration, and which participants engaged in the activity are to be documented in study logs.

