2.3 Scientific Rationale

The overarching objective of the EMIT-2 program is to evaluate how viral aerosol shedding and ventilation interact to facilitate human-to-human influenza transmission and provide insights into correlates of protection in the setting of absent or low hemagglutination inhibiting (HAI) antibodies using a controlled environment. The central hypothesis of EMIT-2 is that inhalation of infectious aerosols (small size infectious particles suspended in air) is the dominant mode of influenza transmission. EMIT-2 will carefully characterize and quantify exhaled infectious aerosols and the indoor environment while assessing the relative effect of planned interventions. For example, in one planned transmission experiment, under conditions with low ventilation and low air hygiene, half of the cohort of recipients will don face shields and use hand sanitizer every 15 minutes while the remaining half of recipients will not don protection or make frequent use of hand sanitizer; all recipients will be instructed to engage in prescribed close-contact activities (e.g., play a board game for 2 hours) with donors who are infected with influenza. As a result, a secondary attack rate of influenza transmissions of approximately 25% is intended to occur under low air-hygiene conditions with a cumulative total of up to 60 hours of exposure of each recipient. The duration of exposure is chosen to match that used in previous trials (Killingley B et al., *J. Infect. Dis.* 2012;205:35–43 and Nguyen-Van-Tam JS et al., *PLoS Pathog.* 2020;16:e1008704).^{4,5} Over the course of approximately 5 influenza seasons, a number of controlled transmission experiments are to be conducted with variable air hygiene conditions. The scientific and engineering technologies and aims of the EMIT-2 program are

contingent upon successfully facilitating secondary influenza infections, i.e., influenza transmissions from index cases (Donors) to exposed contacts (Recipients).

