6.1 General Outline of Activities During Each CHIVITT Cohort

The CHIVITT is to be conducted as a randomized, open, controlled study. Recipient participants for each cohort will enter the study hotel quarantine facility and be housed in individual hotel rooms. After a two-day run-in period to ensure that Recipients are free of preexisting respiratory infections *Exposure Events* will be held in a specially prepared event room.

Recipient participants of each cohort will be randomized to an intervention group or no intervention (Control Recipients, CR). Before entering their first *Exposure Event* each Intervention Recipients (IR) will be trained on how to comply with the intervention. IRs will be required to wear a lightweight plastic face shield, comply with hand hygiene (i.e., using a hand sanitization product every 15 minutes, plus periodic hand washing with soap and water), and avoid face touching during each planned *exposure event*. The face shield may only be removed after leaving the exposure room to go to the bathroom, for other short comfort breaks, and at mealtimes. In these instances, hand hygiene will be used after removing or replacing the face shield; and Donors will not be present. Hand washing with soap and water will be required before meals. IR will be separated from Donors by more than 6 feet during meals. The exposure room will be supervised by a trained member of the study staff who will monitor to ensure that Intervention Recipients wear the face shield continuously, are separated from Donors at meals, and do not touch their faces. Small sticks (e.g., coffee stirrers) will be provided to allow IRs to scratch their faces.

Exposure events are to occur as controlled (prescribed) activities within the exposure room. Exposure events will extend for up to 15 hours per day when Donors are available and able to participate (e.g., 15 hours 8am to 11pm). Each Recipient will participate in up to 60 hours of *Exposure Events* (e.g., 4 days at 15 hours/day) which may be spread over up to 9 or 10 days. During each *Exposure Event* multiple 1-3 hour group activities will be planned and supervised by trained members of the study staff. The group activities are intended to be entertaining and may consist of participating in a card game, board game, foosball game, karaoke, or other group activity which facilitates crowding, loud talking, etc. for potential influenza transmission.

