6.3 Duration of Recipient Participation

Recipients will be requested to be available for participation in a CHIVITT cohort for approximately two contiguous weeks. However, they may voluntarily consent to participate for a longer period. Alternatively, if they join the cohort late to replace a significant number of discharged recipients, they may participate for a shorter period. It is possible that there may be multiple exposure event activities in a single day or there may be days where no exposure event activities are planned (e.g., because there are no donors available with shedding virus). Total time for participation in exposure events will be up to 60 hours over the course of a CHIVITT.

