9.3 Analysis Plan

We will plan to analyze the binary outcome (SAR of influenza infection) using a generalized estimating equation (GEE) with a logistic link function. Individuals sharing a CHIVITT cohort will be considered as a cluster and the dependence will be adjusted by the working correlation in the GEE model. The effect of the interventions will be treated as independent, and the analysis will be controlled for sex, race-ethnicity, and age \geq or < 30 years. We will examine sex as a biological variable for a main effect on infection risk but will not have sufficient power to perform subgroup analysis. R markdown and reproducible statistical analysis will be applied to ensure maximal reproducibility of the data analysis.

Continuous data will be transformed (e.g., Box-Cox transformation) to meet the normality assumption in the analysis. To compare proportions among unpaired samples, we will use logistic regression and adjust covariates as needed. For paired samples, we will use the conditional logistic regression. To examine the group effect on the continuous effect, we will use the general linear model. To test for a trend across

groups, we will use the chi-squared test for trend to compare proportions or Cuzick's test for trend to compare continuous data. Spearman correlation tests will be used to assess correlations between non-binary ordinal variables. The association of immunological measures and other covariates on the risk of infection will be examined using generalized estimating equations (GEE) with a Poisson distribution and robust standard errors to overcome the potential overdispersion. Principal components analysis (PCA) will be used to assess the extent to which variables can be summarized using a smaller number of components. The potential effects of age and sex will be examined in all multivariable models.

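### Section 8.1.2 places IR/CR randomisation at the exposure event and permits a control-only first event, while 6.1 and 2.3 give each Recipient one arm; the sections must be reconciled

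*Protocol*

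**What the plan says.** Section 6.1 allocates people within a cohort: "Recipient participants of each cohort will be randomized to an intervention group or no intervention (Control Recipients, CR". IRs are trained before their first event and must use the shield and hand hygiene at every planned event. The example in 2.3 agrees: "half of the cohort of recipients will don face shields and use hand sanitizer every 15 minutes", and the other half does not.

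Section 8.1.2 names a different unit: "Recipients will be randomized to spray-borne and touch transmission intervention (Intervention Recipients, IR) and control (Control Recipients, CR) within each exposure event". The same section states "Each cohort will experience multiple exposure events over the course of their stay". It then adds an exception under which "the initial exposure event may include only CR to assess the SAR and power of the study design for the remaining events".

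Exposure accumulates over the stay. Section 6.3 says "Total time for participation in exposure events will be up to 60 hours over the course of a CHIVITT", and 6.1 gives four days of 15 hours as an example. The outcome is defined per Recipient in 9.1 (virological, symptomatic or serological). In 9.3 it is a single binary variable: "We will plan to analyze the binary outcome (SAR of influenza infection) using a generalized estimating equation (GEE) with a logistic link function", with the cohort as the cluster.

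**The concern.** Site staff cannot follow 6.1 and 8.1.2 literally at the same time. Under 6.1, arm is a fixed attribute of the person. Under 8.1.2, it is drawn inside an event, and there are several events per cohort. The protocol does not say which arm a Recipient has after being CR in one event and IR in another.

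The control-only exception raises a related problem. If the cohort's first event is run without the intervention, Recipients who are later IR have already had unprotected exposure. That departs from the 6.1 requirement that IRs comply at each planned event.

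The IR vs CR contrast is at stake. It rests on each Recipient having one arm throughout and one outcome. Mixed exposure moves the arms' infection risks together. It often cannot be undone afterwards, because an infection cannot always be tied to one event. Events may fall on consecutive days, 2.5.1 gives an incubation period of 24–48 hours, and one serological criterion is read a month after the stay.

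**Working it through.** **1. The sections side by side**

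| Source | Unit of allocation | Consequence |
|---|---|---|
| 6.1 | Recipients of a cohort | One arm, kept at each planned event |
| 2.3 (example) | Half of the cohort | One arm |
| 8.1.2 | Within an exposure event, several per cohort | Arm can change between events |
| 8.1.2 (exception) | First event may be CR only | A future IR may be unprotected at first |
| 9.2, 9.3 | One arm and one binary outcome per Recipient | Needs a fixed arm |

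**2. The plan's own power figure.** Section 9.2 gives 63 in an intervention group, control SAR 25%, a 76% reduction and 84% power. It also states one-sided testing. The 5% alpha is stated with the other comparison and is assumed to apply here, as are equal arms.

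- IR SAR = 0.25 × (1 − 0.76) = 0.06; difference d = 0.19; mean p̄ = 0.155.
- Null SE = √(0.155 × 0.845 × 2/63) = 0.0645.
- Alternative SE = √((0.25 × 0.75 + 0.06 × 0.94)/63) = 0.0622.
- Power = Φ((d − z × null SE)/alternative SE).
- Two-sided 5% (z = 1.96): Φ(1.02) = 84.7%, which matches the stated 84%.
- One-sided 5% (z = 1.645): Φ(1.35) = 91.1%; with continuity correction 86.3%.

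That the stated one-sided test gives more than 84% is a separate matter. Each version assumes one arm per Recipient. The one-sided figures serve as the baseline below because the section says one-sided.

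**3. Illustration: IRs unprotected for a share f of their exposure.** This assumes infection hazard proportional to exposure time. The values of f are also assumptions: 10% is 6 of 60 hours, and 25% is one 15-hour day of 60.

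IR SAR = 1 − 0.75^f × 0.94^(1−f)

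| f | IR SAR | One-sided power, pooled | One-sided power, continuity-corrected |
|---|---|---|---|
| 0 | 6.0% | 91.1% | 86.3% |
| 10% | 8.1% | 82.4% | 75.4% |
| 25% | 11.2% | 64.8% | 55.7% |
| 50% | 16.0% | 34.4% | 26.6% |

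**4. Illustration: allocation redrawn 1:1 and independently at k events.** The protocol does not fix k. The share of Recipients who stay in one arm is 2 × (1/2)^k: 50% at k = 2, 12.5% at k = 4 and 0.8% at k = 8.

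Steps 3 and 4 illustrate two different literal consequences of 8.1.2. They are not to be combined, and neither is a forecast.

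**The case against.** The strongest reply is that 8.1.2 is loosely drafted and the intended design is the one in 6.1. The section never says that Recipients are allocated again or switch arms. Its phrase could mean that both arms are in the room at every event, which gives concurrent controls. A later bullet in 8.1.2 refers to IRs as individuals already designated by randomisation, which fits a fixed arm. The control-only step may mean the first CHIVITT: 6.1 says the Year 1 study is meant to determine the attack rate, and a single event lasting several hours could hardly estimate an SAR. The exception is also only permissive.

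Much of this stands. Fixed allocation is plausibly the intent. But neither benign meaning is written down. The exception sets the initial event against the remaining events, in a section that has just said each cohort has several, so event-level allocation is still the plain reading.

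A reader might go further and infer that a Recipient's outcome would belong to neither arm. That is too strong. It concerns only Recipients whose allocation changes before infection. Daily molecular testing and the event logs would date many infections roughly; cases found by serology alone are the clearest exception.

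A reader might also infer that control-only Recipients will be pooled into the IR vs CR test and bias it through differences in donors or season. Section 9.3 does not say that they enter that test, and such a rule may sit in an analysis plan that is not shown. A bias calculation of that kind would also need a separate control-only group, which is a different design from redrawing the same Recipients at each event.

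**Conclusion.** The conflict between 8.1.2 and 6.1/2.3 is real and should be fixed. Followed literally, 8.1.2 breaks the basis of one arm and one outcome per Recipient in 9.2 and 9.3, and dilutes the IR vs CR contrast. The documents do not establish that re-randomisation is intended, so the point is a contradiction to resolve before exposure begins. It does not show that the trial's comparison has failed.

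The structural finding depends on no calculation. Its size is illustrative: if IRs were unprotected for 10–25% of exposure, one-sided pooled power would fall from about 91% to about 82–65%. That rests on 63 per arm, SAR 25% vs 6%, and hazard proportional to time. With one allocation kept for the whole stay, the planned contrast and its power are unchanged.

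**What to change.** - In 8.1.2, replace the event-level phrase with: *once, within cohort, before the Recipient's first exposure event, and kept for all events*.
- State that Recipients who join a cohort late (allowed in 6.3) are randomised on entry.
- State whether the initial exposure event means the first CHIVITT. Run any control-only exposure as its own cohort, use it only to estimate the SAR, and exclude it from the IR vs CR test.

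The cost is one corrected sentence and a short clarification. The downside is that control-only data add nothing to the IR vs CR test. Stratifying that test by cohort is an option for the analysis, but its absence is not part of this error.

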8.1.3 Daily Assessments

- Vital signs (including SpO₂, HR, RR, BP, and oral temperature) will be obtained at least twice daily (intended to be at least once in morning and once in afternoon). After the first two days, vital signs will be collected once a day until after exposure to a Donor or at PI discretion.
- A targeted physical examination may be performed, as directed by the medical history, medications, and vital signs assessment. An absence of significant past medical history, concomitant prescription medications, and abnormalities in vital signs will not require a physical examination.
- Once daily collection of a respiratory sample for viral quantitation and performance of a combined influenza and SARS-CoV-2 test (e.g., BioFire Respiratory Virus panel). After the

first two days of negative tests these daily assessments may be paused until after exposure to the first Donor.

- Twice daily completion of a Modified Jackson Score, Investigator Assessment Tool ([Appendix C](#)).
- Once daily completion of a self-reported Symptom Diary, FLU-PRO Survey Instrument and Validation Diary ([Appendix B](#)).
- Additional nasal swab and a saliva sample for research tests. However, these two samples will not be collected between the period after the incubation and before the first donor arrives.
- For Donors, Exhaled breath sampling

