2.5 Potential Risks and Benefits

2.5.1 Potential Risks

Influenza Illness

Common symptoms of common influenza illness includes: body aches or pains, chest congestion, chest tightness, chills, congested or stuffy nose, coughing, diarrhea, difficulty swallowing, eyes sensitive to light, fatigue, feeling dizzy, fever, head congestion, headache, lack of appetite, swollen lymph nodes, nausea, runny or dripping nose, scratchy or itchy throat, shivering, sinus pressure, sleeping more than usual, sneezing, sore or painful eyes, sore or painful throat, stomach ache, sweating, teary or watery eyes.

Moderate complications of influenza, which are unlikely to occur in healthy persons who participate in this study include: sinus infections and ear infections.

Severe complications of influenza, which are also unlikely to occur in healthy persons who participate in this study include: pneumonia, severe dehydration, severe bronchitis, myocarditis, myocardial infarction, pericarditis, Guillain Barré Syndrome/Bell's Palsy, transverse myelitis, encephalitis, worsening of chronic health conditions, admission to hospital, hypoxemia/respiratory failure, arrhythmia/cardiac arrest, and death.

These known risks of complications associated with an influenza infection are to be mitigated by active management by skilled research staff clinicians, including treatment with antiviral therapy (oseltamivir or baloxavir) when indicated. More details of these measures are described in Sections 6.4, 6.5, and 6.6.

Onward Transmission of Influenza Virus

Recipients, through participating in this study, might acquire influenza infection and transmit onwards to contacts outside of the trial, who might include vulnerable individuals. To mitigate this risk, recipients will be isolated and observed for approximately three days after last exposure, which is longer than the 24-48 hour incubation period for influenza, and treated with antiviral therapy prior to discharge if infection is detected.

Blood Draws

Drawing blood may cause transient discomfort and fainting. Lightheadedness or fainting is usually

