4.1 Recipient Eligibility Criteria

Inclusion Criteria

1. Enrolled in the Recipient Protocol (UMB IRB HP-97730)
2. Provides written informed consent, able to comply with the planned study procedures, be available for an up to ~14-day stay for the CHIVITT and have the ability to attend the scheduled follow-up visits.
3. Subjects must be able to comprehend the study requirements, as evidenced by a score of $\geq 70\%$ or better on the comprehension assessment (two attempts permitted).
4. No significant change (for the worse) in general health history or in concomitant medication use, as compared from their responses collected during screening (EMIT-2 Recipient Protocol).
5. Agree not to meet with other participants (recipients or donors) outside of the programmed exposure events during the course of their participation in the CHIVITT.

Exclusion Criteria

1. Female of childbearing potential who has a positive urine pregnancy test within 24 hours of admission to the hotel quarantine unit or is breastfeeding or planning to become pregnant within 2 months after entry into a CHIVITT.
2. Presence of infection with influenza, SARS-CoV-2, or other respiratory pathogens detected via a multiplex nucleic acid amplification test (e.g., Biofire) at admission to the hotel quarantine facility.
3. Within the past 72 hours, presence of influenza-like illness, as defined as fever of $\geq 100.2^{\circ}\text{F}$ AND cough or sore throat, in the absence of an alternative cause.
4. Receipt of any blood products within the past 2 months.
5. Does not agree to provide permission for secondary research use of extra samples collected and stored specimens.
6. Habitual smoker of tobacco, marijuana, or e-cigarettes per self-report. (*Habitual smokers are those who smoke or vape more than four cigarettes, other tobacco products, e-cigarettes or marijuana in a week for more than three months or use an inhaled nicotine or marijuana product more than 3 days a week on average. Edible or patch forms of tobacco or marijuana products do not constitute an exclusion.*)
7. Self-reported or known history of alcohol or drug abuse in the past two years and/or illicit drug use within the last 30 days. (*Prescribed stimulants for the treatment of ADHD and cannabinoids use do not constitute exclusionary criteria*)
8. Has an ongoing symptomatic condition¹ for which the subject has had or has ongoing medical investigations but has not yet received a diagnosis or treatment plan.

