6.9 Discharge Criteria

Subject discharge is planned at approximately 14 days (for Recipient participants) or 2-5 days (for Donor participants) after entry. To be eligible for discharge home, the participant must meet the following criteria: no greater than moderate severity influenza signs or symptoms (Appendix A) and are clinically stable during their stay. In addition, the participant must attest that they feel well enough to provide their own self-care. Otherwise, Recipients will be discharged as described in escalation of care (Section 6.8). Recipients must be at least 2 days post the end of their last exposure event to be eligible for discharge. We may discharge Recipients with a home influenza test to ensure that we do not miss late onset, long latency, influenza infection. However, recipients who have contracted the flu but do not wish to be a donor may be discharged earlier. In this case, they must meet the discharge criteria described above for discharge home. All other instances will be handled as described in Section 6.8.

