17 APPENDIX D: SCHEDULE OF EVENTS

Recipients Participating in a CHIVITT Cohort

Inform of upcoming CHIVITT, ~1 wk prior
 Sign Recipient CHIVITT Consent Form
 Vital signs (SpO₂, HR, RR BP, temp)
 Targeted physical exam
 Nasal Swab, resp virus panel
 Nasal Swab, viral quantification
 Saliva Sample, viral quantification
 Nasal Wash, ~5-10 mL
 Point of care urine pregnancy for FOCBP
 Research Blood, ~10 mL
 Clinical Safety Lab Blood, ~10 mL
 Modified Jackson Score, twice daily
 FLU-PRO survey⁷, once daily
Exposure Events
 Exhaled Breath Sampling
 12-lead electrocardiogram
 Influenza Therapy (anti-viral)
 Adverse Event Reporting

CHIVITT – approx. 14 days on Quarantine Research Unit (w/in 48h) (w/in 72h)								Outpt Clinic Follow-Up ~1 month	Phone Call Follow-Up ~2 months
Pre-Adm	Admission	Daily*	Intermittent or Additional	upon influenza infection	(as requested) Ad Hoc	Discharge, ~Day 14			
X									
	X								
	X	X ¹			X	X ³			
	X	X				X			
	X	X ²	X			X ³			
	X	X ²	X			X ³			
	X	X ²	X			X ³			
	X						X		
	X								
	X		X			X ⁴	X		
				X ⁵	X ⁶				
		X							
		X				X9			
			X						
			X						
				X8					
	X	X	X	X	X	X	X	X	X

* – Daily including Day 1 unless completed as part of admission procedures.

1 – routine daily vital signs are to be performed twice daily (morning and afternoon), except once a day if the Recipient has been observed on the unit for more than two days and has not been exposed to a Donor.

2 – routine daily swabs and saliva may not be necessary prior to first exposure to a Donor and after the first two days of negative tests.

3 – to be performed/collected if not done within the past 12 hours

4 – to be collected if not done within the past 48 hours

5 – these clinical safety labs include: WBC, ALC, Hgb, PLT, ALT, and Cr

6 – these clinical safety labs are to be determined by the requesting clinician; may include: chemistry, hematology, coagulation, cardiac enzymes, and urinalysis

7 – the FLU-PRO survey is completed by the participant

8- Unless consenting to continue in the CHIVITT as a Donor

9 – the FLU-PRO survey won't be administered at discharge if the discharge occurs before 3pm, as the survey becomes available at 3pm.

Donors Participating in a CHIVITT Cohort

Identification of potential influenza case
 Lab-confirmation influenza infection, w/in 48h
 $F \geq 100.2^{\circ}\text{F}$ AND cough or sore throat, w/in 48h
 Sign Donor CHIVITT Informed Consent Form
 Vital signs (SpO₂, HR, RR BP, temp)
 Targeted physical exam

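### Recipient viral testing may stop about 24 hours after admission and restart only after first Donor exposure, so an infection acquired earlier can be counted in the secondary attack rate

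*Protocol*

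**What the plan says.** Section 6.1 places exposure events "After a two-day run-in period to ensure that Recipients are free of preexisting respiratory infections". Section 4.1 excludes a Recipient for "Presence of infection with influenza, SARS-CoV-2, or other respiratory pathogens detected via a multiplex nucleic acid amplification test (e.g., Biofire) at admission". Section 8.1.3 asks for a daily respiratory sample and a combined influenza and SARS-CoV-2 test, but after the "first two days of negative tests these daily assessments may be paused until after exposure to the first Donor". Appendix D, Recipient footnote 2, agrees: "routine daily swabs and saliva may not be necessary prior to first exposure to a Donor and after the first two days of negative tests". The note on the Daily column reads "Daily including Day 1 unless completed as part of admission procedures", so the admission swab can be the Day 1 swab.

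Section 2.5.1 justifies about three days of isolation after last exposure as a period "which is longer than the 24-48 hour incubation period for influenza". Section 6.9 allows a home test at discharge "to ensure that we do not miss late onset, long latency, influenza infection".

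Symptom monitoring is not part of the pause: section 8.1.3 keeps "Twice daily completion of a Modified Jackson Score, Investigator Assessment Tool", with FLU-PRO and vital signs once daily. Section 8.1.4 allows a swab at the investigator's discretion. Section 6.4 treats laboratory-confirmed influenza in a Recipient as counting towards the SAR, with no minimum interval after exposure. No section requires a negative test immediately before the first exposure event.

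**The concern.** The run-in exists to show that Recipients carry no infection when exposure begins. If the last required negative precedes the end of incubation, and the next required swab comes only after Donor contact, the record cannot tell an infection brought into the facility from one acquired in the exposure room. Such a case carries no information about route of transmission, yet it enters the primary endpoint.

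The pause can be long, since Donor arrival is unpredictable (section 8.1.2) and some days may have no Donor (section 6.3). Later laboratory work would not settle the matter. The sample for viral quantitation is paused too, and section 8.1.3 also stops the research swab and saliva until the first Donor arrives. Baseline blood is drawn at admission, so a titre rise looks the same whether infection came before or after exposure.

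Three things are at stake: dilution of the contrast between Intervention Recipients (IR) and Control Recipients (CR), possible imbalance between air-hygiene conditions, and a misleading SAR in the first exposure event, which section 8.1.2 may use to check the design's power.

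**Working it through.** **Timing.** Let I be the incubation period, T the time from admission to the last required negative, and assume that a swab turns positive only when incubation ends. For an infection incubating at admission, with infection time uniform over the incubation, the remaining incubation is uniform on (0, I). The share turning positive after the last test is the mean of max(0, 1 − T/I).

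- T = 48 h, I between 24 and 48 h (section 2.5.1): 0%.
- T = 24 h (admission swab plus Day 2 swab), I uniform on 24-48 h: 1 − 24 × ln(48/24)/24 = 1 − ln 2 = 0.31.
- T = 24 h, I uniform on 24-72 h (72 h is an assumption; section 6.9 concedes long latency but gives no figure): 1 − 24 × ln 3/48 = 0.45.
- T = 48 h, I uniform on 24-72 h: (24 − 48 × ln 1.5)/48 = 0.09.

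So the gap depends on how the two days are counted, or on latency beyond 48 h. These shares are upper bounds for infections first found after exposure, because symptom checks continue.

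**Expected number.** The stretch of pre-admission time left uncovered is I − T. With T = 24 h it is at most 48 − 24 = 24 h (1 day) on the protocol's incubation, and 72 − 24 = 48 h (2 days) if latency reaches 72 h. Assume a weekly community incidence of 0.5% to 2%; the protocol gives no figure.

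- All 175 Recipients: 175 × 0.005 × 1/7 = 0.1 to 175 × 0.02 × 2/7 = 1.0.
- A group of 54: 54 × 0.005 × 1/7 = 0.04 to 54 × 0.02 × 2/7 = 0.31.
- One cohort of 20: 20 × 0.005 × 1/7 = 0.01 to 20 × 0.02 × 2/7 = 0.11.

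**Effect on the contrasts.** Section 9.2 assumes 25% against 5.25% (79% reduction, n = 54) and 25% against 6% (76% reduction, n = 63), each with 84% power. A one-sided 5% comparison of two proportions with continuity correction gives 83.9% for n = 54, matching the plan, and 86.3% for n = 63. A background b of imported infection in both arms changes each rate p to 1 − (1 − p)(1 − b).

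- b = 1/175 = 0.57%, the top of the range: 25.4% against 5.8%, so 79% appears as 77%; 25.4% against 6.5%, so 76% appears as 74%.
- b = 1%, beyond that range: 79% appears as 76% and power at n = 54 falls from 83.9% to 81.5%; 76% appears as 73% and power at n = 63 falls from 86.3% to 84.2%.

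**Initial SAR check.** In a cohort of 20 at 25%, 20 × 0.25 = 5 infections are expected. One import makes it 6/20 = 30%, although the chance of one is low, as shown above.

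**Air hygiene.** Section 6.1 has conditions alternating within a cohort after Year 1 and does not state the order. Imports would surface early, so they would tend to fall in the condition that runs first. Randomising IR and CR within the cohort does not balance this.

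**The case against.** The strongest reply is that the protocol already guards against imported infection. Recipients who test positive at admission are excluded, as are those with influenza-like illness in the previous 72 h. They are then confined to private rooms without guests, so importation largely ends at admission. The pause is optional, discretionary swabs are allowed, and section 9.1.2 describes a physician examination at least daily. A longer pause also gives an incubating infection more time to show itself. All of this stands, and it confines the gap mainly to mild or subclinical infections.

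A reader might infer that the two-day run-in is simply too short, so that an infection incubating at admission will be scored as a secondary attack. The documents do not support that. On the stated 24-48 h incubation, negatives running to a full 48 h cover every such infection. Nor is the three-day isolation a firm benchmark, since section 6.9 requires only at least 2 days after the last exposure event.

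A reader might also note that one imported case moves a group of 54 from 54 × 0.0525 = 2.8 events (5.3%) to 3.8 (7.1%). The arithmetic is right, but such a group expects only 0.04 to 0.31 imports, and imports occur in the comparison group too. It is also tempting to say that an undetected infected Recipient spoils the infective-dose model. Swabs resume after first exposure, infected Recipients give breath samples and the room air is sampled, so that is not shown.

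Finally, detailed attribution rules may sit in a statistical analysis plan that is not at hand. That is fair, but an analysis rule cannot supply a pre-exposure swab that was never taken.

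**Conclusion.** The point holds as a limited gap in ascertainment. The protocol lets viral testing stop on a negative that may be only about 24 h after admission, and requires no test before the first exposure event. An infection acquired earlier can therefore enter the SAR.

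The exposed share is about 31% of infections incubating at admission if the second negative falls at 24 h, and 0% if it falls at 48 h and incubation never exceeds 48 h. Both figures assume uniform incubation and infection times. The expected count, about 0.1 to 1.0 cases over the whole trial, rests on an assumed incidence and on 1 to 2 uncovered days; it includes symptomatic cases that would probably be noticed. The main effect is a dilution of about two percentage points in the apparent reduction at the top of that range. Uneven loading on the first air-hygiene condition and distortion of the initial SAR check are possible but not quantified beyond the cohort figures. This is a cheap improvement worth making, not a threat to the trial's conclusions.

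**What to change.** In section 8.1.3 and Appendix D footnote 2, replace the present restart point with this: the daily molecular test resumes on the day of the Recipient's first exposure event, before that event, and the result is available before entry. Record a positive on that swab as a pre-existing infection, not a secondary attack. Apply the same wording to Recipients who join late.

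Do not remove Recipients from the SAR denominator once they have been exposed. Such a rule acts after exposure and would still miss imports that turn positive later. Instead, show positives found less than 24 h after first Donor contact, the lower end of the stated incubation, in a sensitivity analysis.

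The cost is a wording change, at most about one extra run per Recipient of a test already in use, and a short wait for the result. A swab on the day will still miss an infection that remains undetectable then, so the gap narrows but does not close completely.
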